8.5 VISIT WINDOWS

All scheduled study visits will aim to occur within the time limits specified below and may be adjusted based on pollen count and participant availability.

Table 7. Visit Windows all Participants (See Appendices 1-5)

Visit	Visit description	Visit Window
Visit -4	Screening	October 2020 to January 2022
Visit -3	Rescue medication dispensing visit	April 1 to July 31
Visit -2	Baseline In-season assessments	June 1 to July 31
Visit -1	Baseline NAC	September to January
Visit 0	Randomization – 1 st dupilumab/dupilumab placebo dose	≥ 28 days after Visit -1 and before end of February
Visit 1	1 st SLIT/SLIT placebo dose	≥12 hours from Visit 0 and ≥ 7 days prior to Visit 2.
Visits 2-53	Treatment visits	Every 2 weeks from Visit 0 through week 104 +/- 10 days (with at least 7 days between treatment visits)
Visits 54-65	Observation visits	Every 4 weeks from 108 to 156 +/- 14 days
S1	Out of season visit assessment year 1	January to April
S2, S7, S12	Pre-season visit	April to May
S3, S8, S13	In-season visits	May to August
S4, S9, S14	Out-of-season NAC visits	September to January 1, 2 and 3 calendar years after Visit -1 +/- 14 days
S5, S10, S15	Mechanistic draws post NAC visits	≥ 4 weeks post NAC visit (S4, S9, S14) and before end of February each year
S6, S11	Out of Season visit	January to April

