9.2. Secondary Endpoints

All secondary endpoints denoted as “key” per the multiplicity control testing algorithm (see [Section 8.5](#)) are alpha-controlled. The remaining secondary endpoints, including time points and pairwise comparisons that do not appear explicitly in Table 2: Endpoints with Multiplicity Control of this SAP, will be treated as supportive and are not alpha-controlled; therefore p-values are to be treated as descriptive only.

Unless otherwise noted, all secondary endpoint analyses will be performed on data from the mITT sample using a similar model methodology as per the primary endpoint analysis as described in [Section 9.1.2](#) above. All the same model stipulations apply including the inclusion of fixed effects for treatment arm (all 3 levels), time (i.e. year), and treatment arm by time interaction. Any additional baseline covariates that apply for a given secondary endpoint are noted in each sub-section below.

All pairwise treatment differences will be presented for each year post-treatment, as estimated by the models. Unless otherwise specified, the secondary endpoints will focus on the comparison for:

- Combination of SLIT and dupilumab arm *versus* double-placebo arm

The exploratory endpoints will focus on the remaining pairwise treatment comparisons (see [Section 9.3](#)).

Clinical tolerance endpoints will come from the model estimates at year 3, one year after completion of study treatment; whereas clinical desensitization endpoints will come from the model estimates at year 1 and 2 whilst on study treatment.

If a large departure from normality is found from model assumption testing, then log-transforming the outcome variable of interest prior to modeling or switching to a non-parametric test at each time point, may be performed instead.

9.2.1. TNSS AUC_{0-1hr} at years 1 and 2

The same model as for the primary analysis of TNSS AUC_{0-1hr} above will be used to estimate the LS means treatment difference at years 1 and 2 for the pairwise treatment difference between the combination of SLIT and dupilumab arm *versus* double-placebo arm.

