9.2.6. Seasonal outcome 1: Weekly seasonal symptoms VAS 0-10, Medication scores, and CSMS

Weekly seasonal symptoms (Visual Analogue Scale [VAS] 0-10 cm), medication scores, and combined symptom medication score (CSMS) were collected over the course of 10 weeks from approximately the end of May through end of July, for each year of the study:

- 2021 (baseline season)
- 2022 (year 1)
- 2023 (year 2)
- 2024 (year 3)

Within a given year, the definition of a pollen season will be programmatically derived using Protocol Table 6 as shown below:

	Pollen Season	Peak pollen season	High pollen days
Start of season	1st day of 5 days (out of 7 consecutive days) each of these 5 days with ≥ 3 pollen/m ³ and with a sum of these 5 days of ≥ 30 pollen/m ³	1st day of 3 consecutive days, each with at least ≥ 50 pollen/m ³	The day(s) with at least 50 pollen/m ³
End of season	Last day of series of 5 days (out of 7 consecutive days) with ≥ 3 pollen/m ³ and with a sum of these 5 days of ≥ 30 pollen/m ³	Last day of at least 3 consecutive days, each with ≥ 50 pollen/m ³	

The following two timeframes will be used for analysis:

- only the values collected during weeks which are determined to be “in-season” according to the above table’s definition of “Pollen Season”
- all data collected i.e. up to 10 values per participant per year

The main model for analyses (including for the key secondary endpoint of CSMS) will estimate treatment effects from only the “in-season” weeks, whereas supportive analysis models will use all data collected.

The following three outcomes will be analyzed separately:

- VAS score
- Medication score
- CSMS (combination of VAS and medication score)

The score for each outcome will be analyzed for each of the 10 weeks at each year (including the baseline year). A multiple imputation (MI) approach, similar to the approach described in [Section 9.1.3](#) above, will be used to fill in missing values prior to modelling the score of each outcome at each week per year. Missing at random (MAR) will be assumed given the sporadic missingness of the values at each week.

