The score for each outcome at years 1, 2, and 3 will be analyzed using a multivariate repeated measures model constructed using a direct Kronecker product covariance structure for the distinct repeated effects of year (3 levels) and week (10 levels); see [Section 9.2.5](#) above for more model details. For the baseline season, a mean score for each outcome will be calculated across the “in-season” weeks such that there is a single baseline mean score for each participant; this baseline mean score will be included in the model as an additional covariate. An unstructured covariance matrix product with a second unstructured covariance matrix (SAS option UN@UN) will be assumed to model the correlation among year and week within a participant. If there are convergence issues with this matrix type, then the best fitting and most parsimonious alternative matrix will be used (for example, SAS option UN@AR(1) which models the effect of week using a first-order autoregressive structure). The LS means with associated 95% CIs will be reported for each treatment arm, year, and week.

To estimate a “yearly average” treatment effect for the main analysis, the LS means for each treatment will be calculated from the model estimates using the average of only the “in-season” weeks, for each year. The LS means treatment difference with associated two-sided p-value will be reported for each pairwise difference, for each year (again using only the “in-season” week estimates).

There will be 100 samples imputed for each MI analysis, and results will be summarized across the 100 MI samples. Only participants with a baseline visit (for the score being modelled) will be included in the main analyses. Sensitivity analyses may be considered to include participants where their entirely missing baseline visit will be filled in as part of the MI imputations.

Note as per [Section 8.5](#), only the mean CSMS model results at year 3 (using “in-season” data) will be part of the multiplicity control. Therefore, the supportive model for CSMS (using all data collected) and the models for the component scores of VAS and medication score will be considered supportive and may still have p-values reported for descriptive purposes only.

For the supportive analyses using all data collected, the LS means for each treatment (and their differences) will be calculated from the *same* main analysis model, using the model estimates from all 10 weeks per year.

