9.2.7. Seasonal outcome 2: Weekly rhinitis quality of life scores miniRQLQ measured in-season

Weekly Juniper mini-Rhinoconjunctivitis Quality of Life Questionnaire (miniRQLQ) scores were collected over the course of 10 weeks from approximately the end of May through end of July, for each year of the study using the same collection period as CSMS.

At each week, the average Juniper mini-Rhinoconjunctivitis Quality of Life Questionnaire (miniRQLQ) score will be calculated as the average of the numeric responses (0-6) to all 14 questions in the miniRQLQ questionnaire. Higher scores indicate a worse outcome. If one of the components of the score is missing, then the average miniRQLQ score will also be set to missing at that week.

The miniRQLQ total score will be analyzed for each of the 10 weeks at each year (including the baseline year). A multiple imputation (MI) approach, similar to the approach described in [Section 9.1.3](#) above, will be used to fill in missing values prior to modelling the total score at each week per year. Missing at random (MAR) will be assumed given the sporadic missingness of the values for each year.

The miniRQLQ total score will be analyzed using a multivariate repeated measures model constructed using a direct Kronecker product covariance structure in the same way as CSMS will be modelled (see full model details in [Section 9.2.6](#) above). The “yearly average” treatment effects for the main analysis will be estimated from only the “in-season” weeks as done for CSMS, with a supportive analysis using estimates from all 10 weeks per year.

A covariate for baseline mean miniRQLQ total score will be included in the model.

There will be 100 samples imputed for each MI analysis, and results will be summarized across the 100 MI samples. Only participants with a baseline visit will be included in the main analysis. A sensitivity analysis will be done to include these participants where their entirely missing baseline visit will be filled in as part of the MI imputations.

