9.2.8. Seasonal outcome 3: MRSUI measured in-season and out-of-season

The Modified Rhinitis Symptom Utility Index (MRSUI) questionnaire will be collected twice prior to treatment (at Visit -2 in-season and at Visit 0 out-of-season) and twice (in-season in June/July and out-of-season in November/December) in years 1, 2, and 3. At each visit, the total MRSUI score will be calculated as the sum of the numeric responses to all 10 questions. Higher scores indicate a worse outcome, where the maximum score per visit is 25.

The total MRSUI score will be analyzed using a longitudinal repeated measures model in two ways:

1. Main model for key secondary endpoint and multiplicity control: Modeling only in-season assessments (year 1, year 2, and year 3) with a covariate for baseline in-season total MRSUI score (from Visit -2).
2. Exploratory model: Modeling the in-season assessments minus the prior out-of-season assessment at each year. The time-varying impact of the out-of-season assessments will be accounted for by handling each prior out-of-season assessment as a new baseline value at each year. For example, the first in-season assessment at year 1 will subtract the baseline out-of-season total MRSUI score (from Visit 0).

9.2.9. Seasonal outcome 4: Global Evaluations No. 1 and No. 2 after the season

The Global Evaluation No. 1 questionnaire will be collected after the grass pollen season, annually in years 1, 2, and 3. At each visit, the total Global Evaluation No. 1 score will be calculated as the sum of the numeric responses (0-3) to all 6 questions. Higher scores indicate a worse outcome/severity, where the maximum score per visit is 18.

If 1 or 2 questions were not answered at a particular visit (including baseline), then the total Global Evaluation No. 1 score will be imputed using the following method. If 3 or more questions are missing then the total sum will be left missing.

- Calculate the average of the non-missing question numeric responses for the same participant/visit at which the missing question(s) exist
- Impute the numeric response for the missing question(s) with that average
- Calculate the total sum including the imputed numeric responses for the missing questions

The total Global Evaluation No. 1 score will be analyzed using a longitudinal repeated measures model on data from years 1, 2, and 3 with a covariate for baseline total Global Evaluation No. 1 score.

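### The main CSMS and miniRQLQ analyses (and, by implication, MRSUI) leave out randomised participants who have no 2021 baseline season, at a cost in precision that simple handling of the covariate would avoid

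*SAP*

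**What the plan says.** SAP 9.2.6 covers VAS, medication score and CSMS. It limits the main models to people with a baseline: "Only participants with a baseline visit (for the score being modelled) will be included in the main analyses". For those without one it adds: "Sensitivity analyses may be considered to include participants where their entirely missing baseline visit will be filled in as part of the MI imputations".

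SAP 9.2.7 has the same restriction for miniRQLQ: "Only participants with a baseline visit will be included in the main analysis". There the follow-up is a commitment: "A sensitivity analysis will be done to include these participants where their entirely missing baseline visit will be filled in as part of the MI".

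SAP 9.2.8 fits the main MRSUI model "with a covariate for baseline in-season total MRSUI score (from Visit -2", and gives no rule for a participant who lacks that score.

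Multiple imputation is already part of the CSMS and miniRQLQ analyses. In 9.2.6 it "will be used to fill in missing values prior to modelling the score of each outcome at each week per year", the baseline year included, with 100 imputed samples.

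The default population is set in SAP 9.2: "all secondary endpoint analyses will be performed on data from the" mITT sample, subject to an opening proviso that allows exceptions. The mITT sample (SAP Section 4) requires a baseline nasal challenge and one dose of each treatment, but not a baseline season.

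On timing, the visit-window table in Protocol 8.5 gives screening as "October 2020 to January 2022", confines the in-season baseline visit (Visit -2) to June and July, and requires randomisation before the end of February. SAP 9.2.6 names 2021 as the baseline season and 2022 as year 1.

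**The concern.** Someone screened between August 2021 and January 2022 can complete the baseline nasal challenge, be randomised by the end of February 2022, and contribute three post-baseline seasons. That person belongs to the mITT sample but has no in-season baseline for CSMS, miniRQLQ or MRSUI. The main analyses then set aside all of their outcome data for want of one covariate.

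CSMS, miniRQLQ and in-season MRSUI at year 3 are three of the five endpoints in the survey questionnaire sub-family (SAP 8.5, Table 2), which has its own alpha of 0.05. What is at stake is precision on those endpoints. There is also uneven treatment of one problem: imputing the missing baseline is committed for miniRQLQ, optional for CSMS and not addressed for MRSUI. An optional analysis of an alpha-controlled endpoint leaves a choice open until after unblinding.

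**Working it through.** **1. Can such participants exist?** The documents give three recruitment periods.

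- Synopsis, study design: October 2020 through May 2021. Nobody misses the 2021 season through recruitment timing: 0%.
- Synopsis, study duration: 11 months from October 2020, so to the end of August 2021. With even accrual, 1/11 = 9.1% enter after July.
- Visit-window table, Protocol 8.5: October 2020 to January 2022 is 16 months, 6 of them after July 2021. With even accrual, 6/16 = 37.5%.

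Even accrual is an assumption. No count is stated.

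**2. Which endpoints are touched?** CSMS and miniRQLQ by explicit rule; MRSUI by implication through its covariate. Global Evaluation No. 1 takes its baseline at Visit -1 (Protocol Appendix 1), and No. 2 has no baseline covariate (SAP 9.2.9). So three of five at most.

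**3. Reproduce the plan's own figure.** Protocol 13.6: placebo mean 3.81, SD 1.53 to 1.73, 30 per arm, two-sided 0.05, 80% power. Detectable difference = SD × (1.960 + 0.842) × √(2/30).

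- SD 1.53: 1.107, or 29.0% of 3.81
- SD 1.64: 1.186, or 31.1%
- SD 1.73: 1.251, or 32.8%

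This matches the stated 29% to 33%, and 90/(1 − 0.166) ≈ 108 matches the total. These figures concern the primary endpoint, which the exclusion does not touch. No power is stated for the survey endpoints, so a benchmark has to be borrowed.

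**4. Cost of dropping a share m.** Benchmark: a standardised difference of 0.736, which gives 80% power at 30 per arm by the noncentral t with 58 df (31.7% × 3.81 / 1.64 = 0.736). Then n = 30(1 − m) per arm, and the standard error is multiplied by 1/√(1 − m).

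| Share without baseline | n per arm | SE multiplier | Power at 0.05 |
|---|---|---|---|
| 0% | 30 | 1.00 | 80% |
| 10% | 27 | 1.05 | 76% |
| 20% | 24 | 1.12 | 70% |
| 30% | 21 | 1.20 | 64% |

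At 37.5% (18.75 per arm) the multiplier is 1.26 and power about 60%.

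Under Hochberg with five endpoints the strictest step is 0.05/5 = 0.01. There, by the normal formula with a standardised difference of 0.723, power goes from 59% at 30 per arm to 47% at 24.

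**5. Does keeping them recover the loss?** A simple baseline-adjusted simulation (30 per arm, difference 0.723 SD, 4,000 runs per cell) compared dropping these participants with keeping them, the missing baseline being set to the pooled mean with a missing indicator.

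| Baseline–outcome correlation (assumed) | 20% missing: drop / keep | 37.5% missing: drop / keep |
|---|---|---|
| 0.3 | 70.4% / 79.8% | 60.5% / 79.5% |
| 0.5 | 79.4% / 85.1% | 69.0% / 84.4% |
| 0.7 | 93.0% / 93.6% | 83.8% / 90.6% |

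A separate check under no treatment effect gave type I error of about 0.05 either way. Keeping them recovers power at every correlation tried, though at 0.7 with 20% missing the gain is negligible. This is a stand-in for the principle; it is not the Kronecker-structured model of SAP 9.2.6.

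**The case against.** Several stronger readings are tempting, and the documents do not support them.

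- *Such participants are inevitable.* A reader might infer this from the visit-window table alone. The synopsis recruitment dates would give few or none, and that table lists Visit -2 without describing a route around it. The supportable statement is that they are permitted and anticipated.
- *The SAP contradicts its own mITT population.* The default in 9.2 carries a proviso for exceptions, and 9.2.6 and 9.2.7 state one. It is a declared narrowing, although SAP Section 13 does not list it among the changes from the protocol.
- *Imputation is used where it is not needed and withheld where it is.* The imputation also completes partly missing baseline weeks, which feed a covariate that the repeated-measures likelihood does not handle. Only a wholly missing season is left out.
- *The result is biased.* Baseline availability is fixed before randomisation, so the comparison among those kept remains valid.
- *All the seasonal key secondaries are affected.* Two are affected explicitly and one by implication.

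The strongest defence is practical. The imputation in SAP 9.1.3 starts with an MCMC step run by treatment arm. Ten weeks in each of four seasons is 40 weekly values against 36 participants per arm, and adding people with a whole season missing strains that model further. On this view, an observed-baseline main analysis with an imputed-baseline sensitivity analysis is a defensible order. The point about estimability stands, and is why the fix below does not depend on extending that model. It does not justify dropping people, because one summary covariate can be filled much more simply.

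**Conclusion.** The point holds as a moderate one about precision and consistency. The main CSMS and miniRQLQ analyses exclude anyone without a 2021 season, and the MRSUI model would do so silently.

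The size depends on a number the documents do not give. Over 0% to 30% missing, illustrative power falls from 80% to 64%. That rests on a borrowed benchmark effect, 30 per arm, and a plain two-sided 0.05 instead of the Hochberg thresholds that actually apply. If nobody lacks a baseline, the loss is nil and so is the effect of the change. The primary endpoint and the total of 108 are unaffected.

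**What to change.** - **Main analysis.** For CSMS, miniRQLQ and MRSUI, include all mITT participants with post-baseline data. Fill a wholly missing baseline covariate simply: for example with the pooled mean across arms, with or without a missing indicator, using neither arm nor outcome. Multiple imputation with a model that includes arm and outcomes is an alternative if it can be estimated.
- **Sensitivity analysis.** Keep the baseline-complete analysis as a sensitivity analysis, committed in the same terms for all three endpoints.
- **Reporting.** Give the number without a baseline season by arm, and reconcile the three recruitment periods.
- **Timing.** The note at the end of the SAP was written after database lock. A switch of the alpha-controlled analysis now would be post hoc, so the all-mITT result should be reported as an additional analysis.

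The cost is some SAP wording, a little programming, and reliance on a simple fill of one covariate. No new data are needed.

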9.2.7. Seasonal outcome 2: Weekly rhinitis quality of life scores miniRQLQ measured in-season

Weekly Juniper mini-Rhinoconjunctivitis Quality of Life Questionnaire (miniRQLQ) scores were collected over the course of 10 weeks from approximately the end of May through end of July, for each year of the study using the same collection period as CSMS.

At each week, the average Juniper mini-Rhinoconjunctivitis Quality of Life Questionnaire (miniRQLQ) score will be calculated as the average of the numeric responses (0-6) to all 14 questions in the miniRQLQ questionnaire. Higher scores indicate a worse outcome. If one of the components of the score is missing, then the average miniRQLQ score will also be set to missing at that week.

The miniRQLQ total score will be analyzed for each of the 10 weeks at each year (including the baseline year). A multiple imputation (MI) approach, similar to the approach described in [Section 9.1.3](#) above, will be used to fill in missing values prior to modelling the total score at each week per year. Missing at random (MAR) will be assumed given the sporadic missingness of the values for each year.

The miniRQLQ total score will be analyzed using a multivariate repeated measures model constructed using a direct Kronecker product covariance structure in the same way as CSMS will be modelled (see full model details in [Section 9.2.6](#) above). The “yearly average” treatment effects for the main analysis will be estimated from only the “in-season” weeks as done for CSMS, with a supportive analysis using estimates from all 10 weeks per year.

A covariate for baseline mean miniRQLQ total score will be included in the model.

There will be 100 samples imputed for each MI analysis, and results will be summarized across the 100 MI samples. Only participants with a baseline visit will be included in the main analysis. A sensitivity analysis will be done to include these participants where their entirely missing baseline visit will be filled in as part of the MI imputations.

9.2.8. Seasonal outcome 3: MRSUI measured in-season and out-of-season

The Modified Rhinitis Symptom Utility Index (MRSUI) questionnaire will be collected twice prior to treatment (at Visit -2 in-season and at Visit 0 out-of-season) and twice (in-season in June/July and out-of-season in November/December) in years 1, 2, and 3. At each visit, the total MRSUI score will be calculated as the sum of the numeric responses to all 10 questions. Higher scores indicate a worse outcome, where the maximum score per visit is 25.

The total MRSUI score will be analyzed using a longitudinal repeated measures model in two ways:

1. Main model for key secondary endpoint and multiplicity control: Modeling only in-season assessments (year 1, year 2, and year 3) with a covariate for baseline in-season total MRSUI score (from Visit -2).
2. Exploratory model: Modeling the in-season assessments minus the prior out-of-season assessment at each year. The time-varying impact of the out-of-season assessments will be accounted for by handling each prior out-of-season assessment as a new baseline value at each year. For example, the first in-season assessment at year 1 will subtract the baseline out-of-season total MRSUI score (from Visit 0).

9.2.9. Seasonal outcome 4: Global Evaluations No. 1 and No. 2 after the season

The Global Evaluation No. 1 questionnaire will be collected after the grass pollen season, annually in years 1, 2, and 3. At each visit, the total Global Evaluation No. 1 score will be calculated as the sum of the numeric responses (0-3) to all 6 questions. Higher scores indicate a worse outcome/severity, where the maximum score per visit is 18.

If 1 or 2 questions were not answered at a particular visit (including baseline), then the total Global Evaluation No. 1 score will be imputed using the following method. If 3 or more questions are missing then the total sum will be left missing.

- Calculate the average of the non-missing question numeric responses for the same participant/visit at which the missing question(s) exist
- Impute the numeric response for the missing question(s) with that average
- Calculate the total sum including the imputed numeric responses for the missing questions

The total Global Evaluation No. 1 score will be analyzed using a longitudinal repeated measures model on data from years 1, 2, and 3 with a covariate for baseline total Global Evaluation No. 1 score.

Global Evaluation No. 2 is assessed as a single answer to the question “How was your hay fever this year compared with years before you started immunotherapy treatment?”. The single answer ranges from -3 to +3 as per the following table:

Much better (+3)	Better (+2)	A little better (+1)	The same (0)	A little worse (-1)	Worse (-2)	Much worse (-3)
---------------------	----------------	-------------------------	-----------------	------------------------	---------------	--------------------

The Global Evaluation No. 2 score will be analyzed using a longitudinal repeated measures model on data from years 1, 2, and 3 without any additional baseline covariates.

An exploratory responder analysis may be performed, where the Global Evaluation No. 2 score will be dichotomized as a yes/no responder status for each participant at each post-baseline year. A “responder” will be defined in two ways:

- A score of +2 or better (i.e. better or much better) compared with the years before
- A score of +1 or better (i.e. a little better, better, or much better) compared with the years before

The proportion of responders will be calculated for each treatment arm, separately at each post-baseline year. Each pairwise treatment difference in the proportion of responders will be calculated, along with the corresponding 95% confidence interval (calculated using the Newcombe method).

